1. AMENDMENTS FROM PREVIOUS VERSION(S)

Summary of changes is described in Table 1. No changes spoiling the integrity of this clinical study are included.

Table 1. Summary of Changes

Version/ Date	Associated Protocol Amendment	Rationale	Specific Changes
1.0 05 Jun 2015	Original 28 Jan 2015	N/A	N/A
2.0 6 April 2020	None	Minor changes to clarify the detailed analysis plan	
 • The objective of “to investigate the efficacy of fesoterodine following once daily long-term treatment in Japanese pediatric NDO subjects” was set as secondary objective in accordance with the protocol version 1. • Description of treatment misallocations were minor changed to clarify the treatment group used in the analyses. • Efficacy endpoints of “Mean number of micturitions/24hours”, “Mean number of catheterizations/24hours” and “Mean number of micturitions and catheterizations combined/24hours” were changed to analyze for the subjects with >0 episodes at baseline of Study A0221047, in accordance with A0221047 SAP version 2.0. • Remove an endpoint of “Presence of subtraction test (eg, cough) on urodynamic trace” in accordance with A0221047 SAP version 2.0. • The definition of treatment emergent was changed for AE occur in oxybutinine-treatment period and become more severe; evaluation period of AE was changed from the period in A0221109 to the fesoterodine treatment period from A0221047 in Section 6.2.1. • To clarify that Demographics and baseline characteristics data would be summarized based on baseline information of the A0221047. • To clarify that observed values and change from baseline in efficacy

			
endpoints would be provided in listings.
 
 • To clarify the analysis of onset time of AEs. • Analysis of GPT was changed in accordance with A0221047 SAP version 2.0. • Change visit window definition appropriately.
2.1 9 April 2020	None	Minor error was revised	
 • The date of SAP was changed from 6 Apr 2019 to 9 Apr 2020.

2. INTRODUCTION

Note: in this document any text taken directly from the protocol is *italicised*.

This document describes the statistical analysis plan for the safety and efficacy.

Drug Development Rationale

Antimuscarinic drugs are the cornerstone of pharmacotherapy in the pediatric NDO (neurogenic detrusor overactivity) population, and have been shown to improve intravesicular pressure, and decrease symptoms. Four antimuscarinic drugs (oxybutynin, trospium chloride, tolterodine and darifenacin) have documented results in the pediatric NDO population (Kennelly & DeVoe, 2008).¹ Of these, only oxybutynin is widely approved for use in children, and is available as a once a day extended release (XL) tablet, as well as an immediate release tablet. Although effective, oxybutynin use has been limited by a side effect profile which may have particular relevance in the pediatric population where development (eg, physical, cognitive, psychosocial) is still ongoing.

A particular medication’s effectiveness is highly dependent on patient compliance which is itself dependent on tolerability. Given individual differences in toleration and the limited choice available there is an unmet need for alternative treatments.

Children with NDO therefore represent a disease population with a need for an alternative effective, safe and well-tolerated therapy to help manage the overactive detrusor, reducing or preventing incontinence, as well as the high pressure bladder contractions that can result in UUT (upper urinary tract) deterioration and renal damage.

Other treatments such as alpha blockers, anxiolytics, tricyclic antidepressants, intravesical oxybutynin, botulinum-A toxin, electrical stimulation and biofeedback, may also be used (Coward & Saleem, 2001)² although safety and efficacy have not been reliably demonstrated.

Study Rationale

The primary objective of this study is to investigate the safety and tolerability of fesoterodine PR (prolonged release) tablet 4 mg and 8 mg once daily for 1 year in pediatric NDO subjects

aged between 6-17 years with a body weight >25 kg, and fesoterodine BIC (beads-in-capsule) 2 mg and 4 mg in subjects ≤25 kg.

[figure not shown]
2.1. Study Design

This is a Phase 3, multi-center, open-label long-term extension study in Japanese NDO subjects who participated and completed in the precedent Study A0221047 which is a 24 weeks, randomized, open label study, to investigate the safety and tolerability of fesoterodine.

This study consists of a 28-week open-label treatment period followed by a 4-week follow-up. In addition, subject in the oxybutynin arm of the precedent Study A0221047 will continue the fesoterodine treatment until Week 40 visit in this study, in order to obtain fesoterodine 1 year treatment data (Figure 1 and Figure 2).

Target number of subjects is not determined because this is the safety extension study but approximately 9 subjects are expected to become eligible for the study.

[figure not shown]
Figure 1. Study Design (Subjects who were randomized to Fesoterodine arms in Study A0221047)

() weeks from baseline of Study A0221047

* Week 0 visit is the same visit as Week 24 visit of Study A0221047.

Figure 2. Study Design (Subjects who were randomized to Oxybutynin arm in Study A0221047)

() weeks from baseline of Study A0221047

* Week 0 visit is the same visit as Week 24 visit of Study A0221047.

As a rule, all subjects should continue to receive the allocated dose in Study A0221047 until the end of the trial, unless a safety/toleration problem occurs. But, only if the investigator judges that the continued treatment with low dose (4 mg/day for subjects >25 kg or 2 mg/day for subjects ≤25 kg) is useful to the subject although the high dose (8 mg/day for subjects >25 kg or 4 mg/day for subjects ≤25 kg) is likely to cause some problems with tolerability, and the subject wants the treatment with the low dose, the dosage may be reduced to the low dose at each clinic visits. Dose should not be increased to the high dose.

Subjects >25 kg who cannot swallow tablets are not permitted to take the BIC formulation and are excluded from the study. Even if the body weight of subjects with ≤25 kg at baseline of the precedent Study A0221047 increase >25 kg during Study A0221047 or this study, they should maintain the same dose and formulation.

2.2. Study Objectives

Primary Objective

- *To investigate the safety and tolerability of fesoterodine following once daily long-term treatment in Japanese pediatric NDO subjects.*

Secondary Objective

- *To investigate the efficacy of fesoterodine following once daily long-term treatment in Japanese pediatric NDO subjects.*

3. INTERIM ANALYSES, FINAL ANALYSES AND UNBLINDING

No interim analysis will be planned in this study.

4. HYPOTHESES AND DECISION RULES

4.1. Statistical Hypotheses

There are no statistical hypotheses.

4.2. Statistical Decision Rules

There are no statistical decision rules.

5. ANALYSIS SETS

5.1. Full Analysis Set

The Full Analysis Set will include all subjects who have been enrolled and received at least one dose of study medication and have at least 1 observation in efficacy endpoint data after baseline visit in Study A0221109.

The Full Analysis Set (FAS) will be used for all efficacy analyses.

For all efficacy analyses, the data from Study A0221047 and Study A0221109 will be merged (see the details in [Section 8.1](#)).

5.2. ‘Per Protocol’ Analysis Set

Not applicable.

5.3. Safety Analysis Set

The Safety Analysis Set will include all subjects who have been enrolled and received at least one dose of study medication in Study A0221109.

For analyses of adverse events, the data from Study A0221047 and Study A0221109 will be merged (see the details in [Section 8.1](#)).

5.4. Other Analysis Sets

None.

5.5. Treatment Misallocations

Subjects who are enrolled but never treated in Study A0221109 will not be included in either safety or efficacy analyses. For an enrolled subject who took the incorrect treatment (i.e., a subject who does not start dosing with the randomized dose in Study A0221047), he/she will be reported under the randomized treatment group in Study A0221047 for all efficacy analyses, but will be reported under the treatment they actually received for all safety analyses.

If misallocations already occurred in Study A0221047, the definition determined in Study A0221047 is followed. Hence, for a randomized subject who took the incorrect treatment, he/she will be reported under the randomized treatment group for all efficacy analyses, but will be reported under the treatment they actually received for all safety analyses.

5.6. Protocol Deviations

A full list of protocol deviations will be compiled and reviewed to identify major and minor deviations prior to database closure and a decision taken regarding evaluation for each analysis population.

At enrollment, the investigator will assess patients against the inclusion and exclusion criteria as set out in Sections 4.1 and 4.2 of the protocol.

6. ENDPOINTS AND COVARIATES

6.1. Efficacy Endpoints

- *Maximum cystometric capacity defined as maximal tolerable cystometric capacity or until voiding/leaking begins or at 40 cm H₂O.*
- *Detrusor pressure at maximum bladder capacity.*
- *Presence of IDC (involuntary detrusor contractions)*
- *Bladder volume at first IDC, if present.*
- *Bladder wall compliance (mL/cm H₂O), defined as $\Delta\text{volume}/\Delta\text{pressure}$ during that change in bladder volume.*
- *Mean number of micturitions/24 hours:*

The mean number of micturitions per 24 hours will be calculated as the total number of micturitions divided by the total number of diary days collected at that assessment*. This endpoint will only be calculated for subjects with >0 episodes at baseline of Study A0221047.

- *Mean number of catheterizations/24 hours:*

The mean number of catheterizations per 24 hours will be calculated as the total number of catheterizations divided by the total number of diary days collected at that assessment. This endpoint will only be calculated for subjects with >0 episodes at baseline of Study A0221047.

- *Mean number of micturitions and catheterizations combined/24 hours:*

The mean number of micturitions and catheterizations combined per 24 hours will be calculated as the total number of micturitions and catheterizations combined divided by

the total number of diary days collected at that assessment. This endpoint will only be calculated for subjects with >0 episodes at baseline of Study A0221047.

*Note: The number of diary days collected at that assessment is the number of calendar days that the diary has been completed on (even if this may not be a full 24 hour period). For example, if a diary has been completed for 3 complete days and the morning of the fourth day, this would count as 4 days. This derivation is the same for all the diary endpoints listed 'per 24 hours'.

- *Mean number of incontinence episodes/24 hours.*

The mean number of incontinence episodes per 24 hours will be calculated as the total number of incontinence episodes divided by the total number of diary days collected at that assessment. This endpoint will only be calculated for subjects with >0 incontinence episodes at baseline of Study A0221047.

- *Mean urgency episodes/24 hours if applicable (only for sensate subjects).*

The mean number of urgency episodes per 24 hours will be calculated as the total number of urgency episodes divided by the total number of diary days collected at that assessment. Urgency episodes are defined as Urgency marked as 'yes' in the diary. This endpoint will only be calculated for subjects with >0 urgency episodes at baseline of Study A0221047.

- *Mean volume voided per micturition:*

The mean voided volume per micturition will be calculated as sum of voided volume divided by the total number of micturition episodes with a recorded voided volume greater than 0, regardless of the number of available diary days at that assessment.

Note: missing or zero voided volume will not be included in this calculation

- *Mean volume per catheterization:*

The mean volume per catheterization will be calculated as sum of voided volume divided by the total number of catheterization volume greater than 0, regardless of the number of available diary days at that assessment. Note: missing or zero voided volume will not be included in this calculation

- *Mean volume voided per micturition or catheterization:*

The mean voided volume per micturition or catheterization will be calculated as sum of voided volume divided by the total number of micturition episodes with a recorded voided volume or catheterization volume greater than 0, regardless of the number of available diary days at that assessment. Note: missing or zero voided volume will not be included in this calculation

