2.2. Endpoints

2.2.1. Efficacy Endpoints

- Maximum cystometric bladder capacity defined as maximal tolerable cystometric capacity or until voiding/leaking begins or at 40 cm H₂O.
- Detrusor pressure at maximum bladder capacity.
- Presence of IDC.
- Bladder volume at first IDC.
- Bladder compliance.
- Mean number of micturitions and/or catheterizations/24 hours.
- Mean number of incontinence episodes/24 hours.
- Mean urgency episodes/24 hours if applicable (only for sensate subjects).
- Mean volume voided per micturition and/or mean volume per catheterization.

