9.2.2. Analysis of Efficacy Endpoints

All Efficacy endpoints will be summarized descriptively for FAS by timepoint from baseline visit of A0221047 to final visit of this study, using: N, mean, standard deviation, median, minimum and maximum. Subgroup analyses will be conducted that exclude oxybutynin treatment group in cohort 1 of A0221047 from FAS for all efficacy endpoints if any subjects who were randomized to oxybutynin group in A0221047 are included in FAS. In addition, summary statistics for each cohort and that for each randomized treatment group by cohorts in study A0221047 will be provided as same manner as the above.

Listing tables will be provided at each timepoint from baseline visit of A0221047 to final visit of this study for all efficacy endpoints with subjects information (i.e., subject ID, gender, age, body weight at baseline of A0221047, cohort of A0221047, randomized treatment group in A0221047 and treatment history from the A0221047 start to the end of this study). Also, a summary narrative of efficacy and safety data in each subject will be provided.

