8.2. Statistical Analyses

8.2.1. Analysis of Efficacy Data

For the following efficacy analyses, data will be summarized for the total of treatment groups, each cohort and each treatment group of Study A0221047, using the merged data of Study A0221047 and Study A0221109. *Subgroup analyses will be conducted that exclude oxybutynin treatment group in cohort 1 of A0221047 from the total for all efficacy endpoints if any subjects who were randomized to oxybutynin group in A0221047 are in FAS.*

All efficacy endpoints of continuous data and their change from baseline will be summarized descriptively by each visit according to 8.1.1.

The presence of IDC will be summarized by each visit according to 8.1.2.

Listing tables will be provided at each timepoint from baseline visit of A0221047 to final visit of this study for all efficacy endpoints of observed values and changes from baseline with

subjects information (ie., subject ID, gender, age, body weight at baseline of A0221047, cohort of A0221047, randomized treatment group in A0221047 and treatment history from the A0221047 start to the end of this study).

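### Incontinence and urgency rates are calculated only for children with episodes at the A0221047 baseline, which tilts an uncontrolled change from baseline toward benefit

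*SAP*

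**What the plan says.** SAP Section 6.1 defines the incontinence rate as episodes divided by diary days, then adds: "This endpoint will only be calculated for subjects with >0 incontinence episodes at baseline of Study A0221047". For urgency it adds: "This endpoint will only be calculated for subjects with >0 urgency episodes at baseline of Study A0221047". A parallel sentence stands under micturitions, catheterizations and the two combined.

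The protocol carries no such condition. Section 2.2.1 lists "Mean number of incontinence episodes/24 hours" without qualification, and its only restriction in this group is on urgency: "Mean urgency episodes/24 hours if applicable (only for sensate subjects". Section 9.2.2 sets the population: "All Efficacy endpoints will be summarized descriptively for FAS by timepoint from baseline visit of A0221047 to final visit of this study".

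SAP Section 8.2.1 plans the result as "All efficacy endpoints of continuous data and their change from baseline will be summarized descriptively by each visit according to 8.1.1". Table 3 in SAP Section 8.2.3 gives the analysis set for both endpoints as FAS, with no note of a subset. No planned summary covers children with a zero baseline.

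**The concern.** A child with no incontinence episodes in the baseline diary can have a change of zero or a positive change, never a negative one. The filter therefore removes the subjects who cannot improve, including anyone who becomes incontinent on treatment. The same holds for a sensate child with no urgency recorded at baseline.

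The filter also acts on the children it keeps. A short diary count varies by chance, and a child is kept only if that count was above zero. The baseline mean of the kept group is then too high, and the next diary is lower on average even if nothing has changed.

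The extension has no comparator, so nothing in its own data would reveal either effect. A table headed FAS would omit FAS members without saying so. About 9 subjects are expected, divided by cohort and by up to six treatment labels (SAP Section 8.1), so one or two omitted children can change a row.

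**Working it through.** **Inputs.** The filter is from SAP Section 6.1. Expected enrolment of about 9 is from Protocol Section 9.1. It is consistent with that section's own inputs: 9 cohort 2 candidates plus an unstated few from cohort 1, less 12.5%, gives 10 × 0.875 = 8.75 with one cohort 1 child and 11 × 0.875 = 9.6 with two. The calculation below does not depend on this figure. Diary length is 3 days, minimum 2, from Protocol Section 7.1.2, but that section covers only the Final Visit diary. The same length at the A0221047 baseline is an assumption. Baseline episode rates are not given, so 0.25 to 2 per day is assumed.

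**Spurious change when nothing has changed.** Let the true rate be r per day at both times, with Poisson counts over D diary days.

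- Probability of a zero baseline: exp(−rD).
- Mean baseline among those kept: r / (1 − exp(−rD)).
- Mean at follow-up among those kept: r.
- Apparent change as a share of the kept baseline: −exp(−rD).

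Without the filter the expected change is 0 at every rate.

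| r per day | Kept baseline, D = 3 | Change, D = 3 | Kept baseline, D = 2 | Change, D = 2 |
|---|---|---|---|---|
| 0.25 | 0.474 | −0.224 (−47%) | 0.635 | −0.385 (−61%) |
| 0.5 | 0.644 | −0.144 (−22%) | 0.791 | −0.291 (−37%) |
| 1 | 1.052 | −0.052 (−5%) | 1.157 | −0.157 (−14%) |
| 2 | 2.005 | −0.005 (−0.25%) | 2.037 | −0.037 (−2%) |

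**Rates that differ between children.** If rates follow a gamma distribution with mean m and shape s, the share becomes −(1 + Dm/s)^−(s+1). For D = 3 and shape 1 or 2, the decrease is 16% to 19% at a mean of 0.5/day, about 6% at 1/day and about 2% at 2/day. A simulation at mean 1/day, shape 1 and 3 days gave −0.082/day with the filter and 0.00 without it. The excluded children changed by +0.25/day, and 43% of them had an episode later.

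**Effect of the omitted children (invented example, n = 9).** Seven children go from 2.0 to 1.5 per day. Two start at 0.

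- Filtered summary: (7 × −0.5) / 7 = −0.50/day.
- All nine, if the two stay at 0: −3.5 / 9 = −0.39/day.
- All nine, if the two reach 1.0: (−3.5 + 2) / 9 = −0.17/day.

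**Condition on the direction.** Omitted children change by zero or more. Leaving them out therefore moves the mean toward benefit, or leaves it where it is, whenever the kept children improve or hold level on average. The opposite could occur only if the kept children worsened on average, and by more than the omitted ones.

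**The case against.** **The SAP may depart from the protocol.** Protocol Section 9 allows this, and only major changes to the primary endpoint or its analysis need an amendment. Efficacy uses data merged with A0221047, so matching definitions has value. A zero-baseline child also cannot show benefit, so a subset with room to improve is a sensible thing to show. All of this supports keeping the subset row. It does not support making it the only row. The change log gives parent-study alignment as the reason only for the micturition and catheterization endpoints ("were changed to analyze for the subjects with >0 episodes at baseline of Study A0221047, in accordance with A0221047 SAP version 2.0"), and it records no reason for incontinence or urgency.

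**The size is unknown.** This stands. If nearly every child has several episodes a day, the filter changes almost nothing. Inclusion criterion 1a, which bars subjects with findings of worsening NDO at entry, makes new incontinence before Week 24 less likely in the FAS, though not after it.

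**A sensate flag may not exist.** Neither document defines one or schedules its collection, although the parent study may hold it. This stands, and the fix allows for it.

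Three stronger readings are tempting, and the documents do not support them.

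- *A reader might infer that the micturition and catheterization rates are biased in the same way*, since they carry the condition "This endpoint will only be calculated for subjects with >0 episodes at baseline of Study A0221047". There the filter mainly sorts children by how they empty the bladder. Table 3 of the SAP lists the combined rate, which should be above zero for nearly everyone and still captures a child who starts catheterization. Extending the separate rates to all FAS subjects would add structural zeros, and nothing in the documents makes more catheterization a worse outcome.
- *A reader might infer that new-onset cases can appear nowhere.* Protocol Section 9.2.2 promises a narrative for each subject, and Section 8.3 gives disease worsening as an example of an adverse event. The SAP does not carry the narratives over, however, and its listings are of endpoints that it does not calculate for these children.
- *A reader might infer that regression to the mean will be claimed as efficacy.* The SAP has no hypotheses or decision rules and plans only descriptive changes. Regression to the mean affects any single-arm change from baseline. The filter adds to it.

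**Conclusion.** The point holds for incontinence and urgency. The SAP narrows the protocol's population, Table 3 does not show this, and the selection is one-sided in an analysis with no control. The mean change shifts toward benefit unless the retained children themselves worsen on average.

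On the assumptions above, the spurious part is material at about 1 episode per day or fewer and negligible at 2 per day or more. The documents do not show which case applies. Since efficacy is a secondary, untested objective, this is a change that should be made rather than a threat to the study's primary purpose.

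**What to change.** In SAP Sections 6.1 and 8.2.1 and in Table 3 of Section 8.2.3:

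1. Summarise incontinence for all FAS subjects with diary data.
2. Summarise urgency for all sensate FAS subjects with diary data, using the parent study's sensate classification if it is available. Otherwise use all FAS subjects with urgency diary data.
3. Keep the subset with episodes at baseline as a second, labelled row, for consistency with the A0221047 SAP.
4. Report how many subjects go from 0 to above 0 on each endpoint.

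Leave the micturition, catheterization and combined rates unchanged.

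The cost is a few SAP sentences and one extra row and one count per endpoint, from diaries already planned. The small downside is a main row that differs from the parent-study convention, and the second row covers that.
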